#### 13.2.1. POST-ANGIOPLASTY ANGIOGRAPHIC REQUIREMENTS

Final angiographic eligibility of subjects for study device treatment will be determined post pre-enrollment balloon angioplasty and include but are not limited to the following target lesion measurements (by visual estimate):

- Target lesion residual diameter stenosis <30%
- Presence of dissection(s)
- Absence of thrombus
- Normal artery branching and/or target vessel reconstitution

In addition, other lesion measurements and balloon details will be recorded during Pre-Enrollment Balloon Angioplasty and include but are not limited to the following:

- Total number of dissection(s) visualized
- Dissection characteristics (by visual estimate) for each dissection visualized including;
  - Dissection Type (A through F)
  - Dissection Length
  - Vessel Location
  - Ruler Location
- For each vessel segment inflation:
  - Balloon name/Manufacturer, Length, Diameter
  - Vessel location
  - Ruler location
  - Max Pressure (atm) (across all inflations)
  - Inflation Duration at Max Pressure (across all inflations)
  - Max Inflation Diameter (across all inflations)

### 13.3. STUDY DEVICE TREATMENT

Subjects who meet all inclusion and angiographic inclusion criteria, and do not meet any exclusion or angiographic exclusion criteria will be deemed eligible for Study Device Treatment.

#### 13.3.1. ENROLLMENT (INTENT-TO-TREAT)

A subject is defined as an intent-to-treat (ITT) and officially enrolled in the study once the Tack Endovascular System is advanced through the introducer sheath. Subjects in whom at

least one Tack implant is not placed, will be exited after 30 days. Subjects in whom at least one Tack implant is placed will be followed for 36 months.

In addition, the per-protocol (PP) population will be defined as ITT subjects with evaluable data that have met the definition for device success, excluding subjects with major deviations such as:

- A major inclusion/exclusion criterion deviation; or
- A major procedural deviation

The criteria for deviations meeting the classification of “major” will be defined by an independent designee before study endpoint data is available for statistical analysis.

### 13.3.2. TREATMENT RECOMMENDATIONS

The lesion considered for Tack implant placement is assessed with a minimum of two angiographic views, an anterior-posterior view and a 45-degree oblique view, for optimal visualization of the dissections. All dissections identified for treatment with the Tack implant will be categorized by type by the operator as described in **Section 13.2.1**. If there are no dissections present, the subject may not be enrolled and Tack implants should not be placed.

Intact Vascular recommends deployment of a Tack implant to the distal edge of the target dissection. If additional Tack implants are required, the operator should continue proximally to the next planned deployment site. A minimum gap distance of 4.0mm between Tack implants (end to end) is recommended. Overlapping Tack implants is not permitted.

Please refer to the Instructions for Use (IFU) for detailed instructions regarding recommended criteria for Tack Endovascular System placement.

### 13.3.3. POST-STUDY DEVICE TREATMENT MEASUREMENTS

The following information should be recorded Post-Study Device Treatment:

- Number of Device Systems used to treat subject and associated lot numbers
  - Number of Tacks deployed from Device
  - Whether device was successfully withdrawn
- Number of Tack implants deployed
  - Ruler and vessel location of each deployed Tack implant
  - Number of Tack implants deployed to treat each dissection and whether it was successful in treating respective dissection identified in **Section 13.2.1**

### 13.4. POST- TACK DILATION

Post-dilation of all deployed Tack implants is required to seat the anchors of the Tack implant. Use of a new standard balloon catheter is required to reduce the risk of contact with deployed Tack implants while advancing the balloon catheter into place.

#### 13.4.1. RECOMMENDATIONS

After Tack implant placement, it is recommended that post-dilation of all deployed Tack implants be performed using the following criteria.

- The balloon diameter for post-dilation should use the same balloon diameter and pressure used during angioplasty prior to Tack implant placement and should be the shortest length possible
- Post-Dilation Duration at Max Pressure: A minimum of 120 seconds.

Please refer to the Instructions for Use (IFU) for detailed instructions regarding post-Tack implant placement balloon angioplasty recommendations.

#### 13.4.2. FINAL TREATMENT RESULTS

The following information should be recorded after post-dilation and upon completion of index procedure and includes but is not limited to:

- For each vessel segment receiving post-Tack inflation:
  - Balloon name/Manufacturer, Length, Diameter
  - Vessel location
  - Ruler location
  - Max Pressure (atm) (across all inflations)
  - Inflation Duration at Max Pressure (across all inflations)
  - Max Inflation Diameter (across all inflations)
  - Final residual diameter stenosis of target lesion(s) treated with Tacks
- Bailout stent occurrence (post-study device treatment)
  - If applicable, bailout stent device details will be recorded
- Study Device Procedure time (defined as the time the first Tack Endovascular System is advanced through the introducer sheath to the time of withdrawal of last post-Tack dilation PTA balloon catheter)
- Adverse event occurrence
- Device event occurrence

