**Table 4. TOBA-BTK Trial Baseline Clinical Assessment of Target Limb**

Parameter	Safety Sample N = 35	Performance Sample N = 32
Target Limb		
Left	40.0% (14 / 35)	34.4% (11 / 32)
Right	60.0% (21 / 35)	65.6% (21 / 32)
Number of Patent Tibial / Peroneal Vessels in the Target Limb		
1	42.9% (15 / 35)	46.9% (15 / 32)
2	42.9% (15 / 35)	37.5% (12 / 32)
3	14.3% (5 / 35)	15.6% (5 / 32)
ABI treated leg (mean ± stdev) (minimum, median, maximum)	0.95 ± 0.42 (35) (0.0, 0.94, 1.9)	0.91 ± 0.41 (32) (0.0, 0.93, 1.9)
TBI treated leg (mean ± stdev) (minimum, median, maximum)	0.49 ± 0.30 (24) (0.0, 0.47, 1.1)	0.47 ± 0.28 (23) (0.0, 0.46, 1.1)
Subject Pain Symptoms for Target Limb (check all that apply)		
No Leg Pain	48.6% (17 / 35)	46.9% (15 / 32)
Rest pain	28.6% (10 / 35)	28.1% (9 / 32)
Pain on exercise	28.6% (10 / 35)	31.3% (10 / 32)
Rutherford Clinical Category for Target Limb		
4	11.4% (4 / 35)	12.5% (4 / 32)
5	88.6% (31 / 35)	87.5% (28 / 32)

The mean pre-PTA percent diameter stenosis per lesion was 72.3%± 17.4 and 73.0%± 17.8, for the safety and performance samples, respectively. Total occlusion comprised eight of the lesions (22.2% safety sample, 24.2% performance sample). Of all dissections reported (Safety Sample), the most frequently reported worst dissection grade was B (40.5%) followed by A (35.7%), C (19.0%), and D (4.8%). The worst post-PTA dissection grades pre-Tack at Tack sites were A (21.2%), B (60.6%), and C (18.2%). The mean number of Tack implant(s) used in the Performance Sample was 2.8±2.0 with a range of 1 to 12 per lesion. Tack implant(s) were successfully delivered in 33/36 (91.7%) lesions. Three individual lesions in three subjects were not successfully treated as in each case, the catheter was not able to be advanced to the lesion location. Of the successfully placed Tack implant(s), the post-Tack implant dissection grade was 0 in 32/33 (97.0%) and B in 1/33 (3.0%). Tack implant locations to treat the dissections included anterior tibial artery (32.6%), tibio-peroneal trunk (30.4%), peroneal artery (20.7%), and posterior tibial artery (16.3%). In greater than 89.7% of the Performance Sample vessels, the Tack was placed on the proximal edge of the dissection being treated and in 76.9% of the vessels the Tack was placed on the distal edge of the dissection.

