### 19.5. OBSERVATIONAL ENDPOINTS

- Device Success: Successful deployment of the Tack implant(s) at the intended target site(s) and successful withdrawal of the delivery catheter from the introducer sheath.
- Target Lesion Success: Demonstrated target lesion patency [ $<30\%$  residual diameter stenosis (DS), by visual estimate] without the use of a bailout stent within the target lesion upon completion of the index procedure. This will be assessed for all lesions treated with a Tack implant. In addition, target lesion success will also be analyzed by lack of bailout stent to tacked segment only. Multiple target lesions treated as one lesion with PTA will be analyzed as one lesion.
- Procedural Success: Demonstrated target lesion patency ( $<30\%$  residual DS, by visual estimate) without the use of a bailout stent within the target lesion and without the occurrence of MALE+POD upon completion of the index procedure
- Amputation-free survival (AFS): Freedom from above-ankle target limb amputation or all-cause death at 6 and 12 months
- Freedom from MALE at 12 months + POD at 30 days
- Target lesion(s) tacked segment(s) patency at 12 months defined as the presence of blood flow using duplex ultrasound.
- Target Limb Salvage defined as freedom from any above-ankle target limb amputation at 12 months
- Assisted primary target lesion Tacked segment patency (flow vs. no flow) at 6 and 12 months
- Secondary target lesion Tacked segment patency (flow vs. no flow) at 6 and 12 months
- PSVR patency at 6 and 12 months [Freedom from binary restenosis defined as Peak Systolic Velocity Ratio (PSVR) of  $\geq 2.5$  and/or angiographic percent diameter stenosis of  $\geq 50\%$ ] assessed for the following:
  - Target Lesion(s), defined as the entire contiguous arterial segment treated with angioplasty, inclusive of an additional proximal and distal margin of 5 mm
  - Tacked Segment(s), defined as the Tack device and 5 mm of artery proximal and distal to each Tack. If Tacks are within 10 mm of each other, they will be considered as a single tacked segment for the purposes of this patency assessment.
- Clinically-driven target lesion revascularization (CD-TLR) through 6 and 12 months
- Clinically-driven target vessel revascularization (CD-TVR) through 6 and 12 months

- All-cause death through 6 and 12 months
- Any Target vessel revascularization (TVR) through 6 and 12 months
- Any Target lesion revascularization (TLR) through 6 and 12 months

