#### 21.9. CENTRAL CORE LABORATORIES

To ensure that the clinical data and images are analyzed in a controlled, non-biased manner and that the results are analyzed using a standardized process, all angiograms, duplex ultrasound studies and x-rays obtained during this study will be submitted to a respective central core lab for analysis.

The core labs will be responsible for analyzing the angiograms, duplex ultrasound and x-ray images according to the study eligibility criteria, the study endpoints and requirement measurements according to this study protocol. Feedback will be provided to the sites and Sponsor regarding the quality of the tracings and images and for providing a written summary report of all angiogram, duplex ultrasound and X-ray results to the study Sponsor.

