Type E	Persistent luminal filling defect with delayed run-off of the contrast material in the distal lumen.
Type F	Filling defect accompanied by total occlusion.
Drug-Coated Balloon (DCB)	Drug-coated balloon catheter used for percutaneous transluminal (balloon) angioplasty.
Duplex Ultrasound (DUS)	A form of medical ultrasonography that includes the following elements on the same screen (“duplex”) to facilitate interpretation 1) B-mode, pulsed Doppler display to visualize the structure within a vessel and 2) Color-Doppler display to visualize the blood flow and hemodynamics within a vessel.

Term	Definition
DUS Flow / No Flow	
DUS Flow - Visualization of color Doppler and pulsed Doppler detectable flow within an arterial segment
 
DUS No Flow – Absence of color Doppler and pulsed Doppler detectable flow within an arterial segment with evidence of flow within the corresponding venous segment

Index Procedure	The interventional procedure during which the study device is advanced through the introducer sheath and the subject is enrolled.
Intent-to-treat (ITT) subjects	A subject is defined as an intent-to-treat (ITT) patient and officially enrolled in the study once the Tack Endovascular System is advanced through the introducer sheath.
Lesion Success	Demonstrated target lesion patency (<30% residual DS, by visual estimate) without the use of a bailout stent. This will be assessed for all lesions treated with a Tack. In addition, target lesion success will also be analyzed by lack of bailout stent to tacked segment only. Multiple target lesions treated as one lesion with PTA will be analyzed as one lesion.
Limb Salvage	Freedom from any above-ankle target limb amputation
Major Adverse Event (MALE)	Above-ankle target limb amputation or major re-intervention to the target lesion(s) (defined as new bypass graft, jump/interposition graft revision, or thrombectomy / thrombolysis)
Major Re-intervention	New bypass graft, jump/interposition graft revision, or thrombectomy / thrombolysis occurring after the index procedure
Major Amputation	Any above the ankle amputation to the target limb.
Minor Amputation	Any below the ankle amputation to the target limb (digital or transmetatarsal (ray or complete))

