Primary Safety Endpoint	Freedom from BTK MALE+POD at 30 days. Composite of all-cause death, above-ankle target limb amputation or major re-intervention to the target lesion(s) (defined as new bypass graft, jump/interposition graft revision, or thrombectomy / thrombolysis)
Procedural Success	Demonstrated target lesion patency (<30% residual DS, by visual estimate) without the use of a bailout stent and without the occurrence of MALE+POD upon completion of the index procedure.
Restenosis	Reoccurrence of narrowing or blockage or target lesion.
Rutherford Classification	Clinical scale identifying three grades of claudication and three grades of critical limb ischemia ranging from rest pain alone to minor and major tissue loss.
Class	Clinical Description
0	Asymptomatic —no hemodynamically significant occlusive disease
1	Mild claudication
2	Moderate claudication
3	Severe claudication
4	Ischemic rest pain
5	Minor tissue loss—nonhealing ulcer, focal gangrene with diffuse pedal ischemia
6	Major tissue loss—extending above TM level, functional foot no longer salvageable

Term	Definition
Secondary Efficacy Endpoints:	
 
▪ Target lesion(s) tacked segment(s) patency at 6 months defined as the presence of blood flow using duplex ultrasound. If angiography is available within the 6-month follow-up visit window, it should be used in place of the duplex ultrasound. Evidence of no blood flow within the Tacked segment indicates restenosis/loss of patency.
 
▪ Target Limb Salvage defined as freedom from any above-ankle target limb amputation at 6 months.
 

Secondary Target Lesion Tacked Segment Patency	Secondary patency (freedom from total occlusion) achieved with the use of an additional or secondary surgical or endovascular procedures. In all cases, freedom from total occlusion is confirmed by angiography or DUS (flow vs. no flow) if angiography was not performed.
Serious Adverse Device Event (SADE)	A serious adverse device effect (SADE) is defined as an adverse device effect (ADE) that results in any of the consequences characteristics of a serious adverse event (SAE). (See ADE)

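### Target Lesion Success and Procedural Success rest on a visual stenosis reading in an open-label single-arm trial; score them on the core-lab reading and show both (minor, cheap improvement)

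*Combined protocol and SAP*

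**What the plan says.** Section 19.5, repeated in the synopsis and Section 6.3, defines Target Lesion Success by a <30% threshold on "residual diameter stenosis (DS), by visual estimate] without the use of a bailout stent within the target lesion upon completion of the index procedure". Procedural Success uses the same threshold: "residual DS, by visual estimate) without the use of a bailout stent within the target lesion and without the occurrence of MALE+POD". The glossary in Section 24 keeps the visual basis for both: "Demonstrated target lesion patency (<30% residual DS, by visual estimate) without the use of a bailout stent" for lesion success and "Demonstrated target lesion patency (<30% residual DS, by visual estimate) without the use of a bailout stent and without the occurrence of MALE+POD" for procedural success.

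Section 13.4.2 lists "Final residual diameter stenosis of target lesion(s) treated with Tacks" among the items recorded after post-dilation. That line names neither a reader nor a method; the visual basis comes from the definitions.

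For imaging, Section 9.2 sends all index imaging of enrolled subjects to the angiographic core laboratory within 3 days. Section 21.9 adds that "all angiograms, duplex ultrasound studies and x-rays obtained during this study will be submitted to a respective central core lab for analysis", gives unbiased and standardized analysis as the reason, and has the core labs work to the eligibility criteria and the study endpoints. Section 13.1 is narrower: the only task it names for the core lab on index angiograms is to identify and type post-PTA dissections.

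**The concern.** A residual stenosis judged by eye, at the site, at the end of an open-label procedure is open to a favourable reading, and success turns on a single cut-point. There is no control arm in which the same reading habit would cancel out.

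The entry rule sharpens this. Angiographic inclusion criterion 8 (Section 7.4.2) and Section 13.2.1 already require <30% residual stenosis by visual estimate after PTA. The stenosis part of both endpoints therefore asks the site to confirm, shortly afterwards and by the same method, something it has just certified. That leaves this component little room to inform unless an independent read is shown as well.

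At stake is how far two published acute success rates can be trusted. The study supports a premarket application (Section 16.3), and results for all pre-specified outcomes are to be posted (Section 21.16).

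**Working it through.** **The passages side by side**

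1. *Who reads.* The definitions say visual estimate and name no reader. Because the value is recorded with the procedural data, a reading at the site is the natural meaning. That it is the implanting operator's own reading is an inference.
2. *Blinding.* Section 19.1 describes a single-arm, non-blinded study.
3. *What the core lab has.* It receives all index imaging (9.2) and all angiograms (21.9).
4. *What the core lab measures.* A final percent diameter stenosis read is implied by 21.9, because residual stenosis <30% is both an eligibility criterion and part of two endpoints. It is stated nowhere; 13.1 names only dissections.
5. *Which read prevails.* Section 21.7.2 makes the Clinical Events Committee's determination primary except for endpoints derived from core-lab analysis. Nothing says whether these two endpoints are of that kind, and their definitions point to the visual value.
6. *What depends on the result.* Observational endpoints are summarized descriptively (19.8.4). Study success uses only the two primary endpoints (19.12). The hierarchical step concerns 6-month patency (19.13). The per-protocol set uses Device Success, which has no stenosis criterion (19.2).

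**Arithmetic**

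The documents give no target rate, alpha or power for either endpoint and no rate of disagreement between visual and core-lab reads, so there is no plan figure to reproduce. The following only shows how sensitive a reported rate would be.

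Assumptions: n = 232 (planned enrollment, Section 19.6), one lesion per subject, and visual success v = 97%. Let f be the share of visual successes that the core lab would read as ≥30%. The core-lab rate is then r = v × (1 − f). Counts are rounded and intervals are 95% Wilson.

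- f = 0: r = 0.970, 225/232 = 97.0%
- f = 2%: 0.97 × 0.98 = 0.951, 221/232 = 95.3% (91.7 to 97.3)
- f = 5%: 0.97 × 0.95 = 0.922, 214/232 = 92.2% (88.1 to 95.0)
- f = 10%: 0.97 × 0.90 = 0.873, 203/232 = 87.5% (82.6 to 91.2)
- f = 20%: 0.97 × 0.80 = 0.776, 180/232 = 77.6% (71.8 to 82.5)

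So 5% one-directional disagreement costs 225 − 214 = 11 subjects, about 5 points. In the other direction there is little room: only 232 − 225 = 7 subjects are visual failures, so the rate could rise by at most 7/232 = 3.0 points. It would rise by less if some of them failed through a bailout stent or a MALE+POD event.

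**The case against.** The strongest reply is that the visual definition is deliberate, disclosed and matched to eligibility. Lesions enter on a visual <30% after PTA. If only the final result is read by the core lab, a lesion that the core lab would already have put at ≥30% before any Tack was placed counts as a failure of a device meant to repair dissections. This stands as a reason not to replace one number with another and stop there. It is answered by reporting both reads and the core-lab value after PTA and before Tack placement.

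A second reply is that no core-lab final stenosis read is shown to exist, since the core-lab protocol is a separate document. This stands in part: Section 21.9 implies the read but does not state it, so it must be confirmed.

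A third is that the other components, bailout stenting and MALE+POD, do not depend on the stenosis reading, and that both endpoints are descriptive. This stands in full and sets the severity.

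A reader might go further and take the pilot as evidence of reader bias. Section 4.2 reports: "The mean pre-PTA percent diameter stenosis per lesion was 72.3%± 17.4 and 73.0%± 17.8" (safety and performance samples). Pilot entry required ≥70% stenosis or occlusion, and 8 of 36 lesions were occluded. Counting occlusions as 100%, the mean could not be below 8/36 × 100 + 28/36 × 70 = 76.7%, and the implied mean of the non-occluded lesions is (72.3 − 22.2)/0.778 = 64.4%. The arithmetic is right but the inference fails. Section 4.2 does not say who read those values, so two different readers are not established. Unmet entry criteria would explain the gap equally well. The figures also concern stenosis before PTA, and say nothing about the size or direction of error near 30% after treatment.

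**Conclusion.** Both acute success rates may be subject to favourable reader bias, because the threshold is read by eye at the site, without blinding, by the method that admitted the lesion. The documents support a risk, not an estimate. The 5-point loss per 5% disagreement shown above rests on assumed v and f and on disagreement running in one direction.

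A reader might also model the effect. If core-lab final stenosis were normal with mean 20% and SD 10%, a 5-point favourable shift would raise success from 84% to 93%; other assumed means, SDs and shifts give gains of 2 to 21 points. The documents give no distribution of final stenosis and no shift, so none of this can be stated as the size of the bias, nor can it be said that results cluster near 30%.

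Nor do the documents support a claim that the trial's conclusions are at risk. The primary tests, the 6-month patency test, the sample size and study success do not use this reading. Severity is minor: a cheap improvement.

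**What to change.** Before endpoint data are available:

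- In the synopsis and Sections 6.3, 19.5 and 24, score the <30% criterion of both endpoints on the core-lab final percent diameter stenosis from the index angiograms.
- Confirm that the core-lab protocol includes this measurement, and add it if it does not.
- Report the visual-estimate rates alongside, with a cross-tabulation of the two reads.
- Show the core-lab stenosis after PTA and before Tack placement, so that lesions already at ≥30% before the device are visible.
- Where no core-lab read is possible, use the visual value and state how many lesions this affects.

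The cost is definition wording, a little more analysis, possibly one added core-lab measurement on images already submitted, and perhaps slightly lower reported acute success rates. Eligibility and patient management do not change.
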